10.3 Statistical Analyses

The SAP will be developed and finalized before database lock.

Below is a summary of the timing and methods for the planned statistical analyses. To preserve study integrity, the final analysis will be conducted and reported following the end of study, as defined in [Section 5.3.1](#).

10.3.1 Planned Analyses

10.3.1.1 Interim Analysis and Early Stopping Guidelines

For Part A, two interim analyses are planned when approximately 80 and 160 subjects complete their week 16 assessments, respectively. [REDACTED]

[REDACTED]

The interim analyses will be performed by an independent statistician. The numerical results of the interim analyses will not be accessible to the study team. The study team will only know whether the study will continue or will be terminated based on the results.

For Part B, no interim analyses will be performed.

10.3.1.2 Primary Analysis

The primary analysis will occur when the primary completion date described in [Section 5.3.1](#) has been observed, and the data have been entered, cleaned, and locked. The objective for the primary analysis is to assess safety and efficacy through week 16 for Part A only.

10.3.1.3 Exploratory Analysis for Part B

For Part B of this study, an exploratory analysis will occur when all subjects have completed the week 16 assessments, and the data have been entered, cleaned, and locked. The objective for this exploratory analysis is to assess safety and efficacy through week 16 for Part B only.

10.3.1.4 Final Analysis

The final analysis will occur when the end of study date described in [Section 5.3.1](#) has been observed, and the data have been entered, cleaned, and locked. The final analysis will analyze efficacy and safety over the entire study period for Part A and Part B. For this analysis, Part A and Part B will be analyzed separately. However, some additional analyses (eg, adverse event summaries) may combine Part A and Part B; if performed, these analyses will be described in the SAP.

[figure not shown]
10.3.2 Methods of Analyses

10.3.2.1 General Considerations

Subject disposition, demographics, and baseline disease characteristics will be summarized descriptively by randomized treatment group. For categorical endpoints, the descriptive statistics will contain frequency and percentage. For continuous endpoints, the descriptive statistics will include the number of observations, mean, standard error, standard deviation, median, first quartile, third quartile, minimum, and maximum.

For Part A, the treatment effect for the primary analysis of the primary endpoints will be tested using a Bonferonni-based gatekeeping procedure to control the family-wise 2-sided type I error rate at 0.05. The procedure splits the α of 0.05 equally to test in parallel tezepelumab 420 mg SC Q2W versus placebo, and tezepelumab 280 mg SC Q2W versus placebo for IGA 0/1 and EASI 75 sequentially within each parallel path. If one of the parallel paths rejects the 2 hypotheses sequentially, and the other path has at least 1 hypothesis not rejected, then the unspent α of 0.025 from the successful path will be propagated to the unsuccessful path to retest the 2 hypotheses sequentially at a level of 0.05. This procedure is illustrated in [Figure 10-1](#).

Figure 10-1. Alpha Split Between Two Doses of Interest

For all other endpoints in Part A and B, significance testing, if performed, will be considered descriptive.

10.3.2.2 Efficacy Analyses

Endpoint	Statistical Analysis Methods
Primary	For the primary endpoints of IGA 0/1 and EASI 75 at week 16, the treatment effect will be tested using a logistic regression model adjusting for covariates specified in Section 10.2.2 . From this model, odd ratios and 95% CIs will be reported comparing each tezepelumab dose group to placebo. In addition, the percentage of subjects in each treatment group with a response and the difference in the percentage of subjects responding between each tezepelumab dose group and placebo will be summarized with a 95% confidence interval.
Secondary	The analysis of secondary endpoints will be descriptive and details will be provided in the SAP.
Exploratory	Details of the analysis of exploratory endpoints will be specified in the SAP.

10.3.2.3 Safety Analyses

10.3.2.3.1 Adverse Events and Disease-related Events

Subject incidence of all treatment-emergent adverse events will be tabulated by system organ class and preferred term. Tables of fatal adverse events, serious adverse events, adverse events leading to withdrawal from investigational product or other protocol-required therapies, and significant treatment-emergent adverse events will also be provided. Subject incidence of disease-related events, if applicable, will be tabulated by system organ class and preferred term.

10.3.2.3.2 Laboratory Test Results

Laboratory parameters will be summarized descriptively by treatment group and visit. Grade 0 through 4 toxicities, as defined by the CTCAE, version 5.0 (or most recent version) will be presented for each laboratory parameter when available.

10.3.2.3.3 Vital Signs

Vital signs will be summarized by treatment group.

10.3.2.3.4 Exposure to Investigational Product

Exposure to investigational product will be summarized by treatment group. The summary of study drug exposure will include descriptive statistics for the number of study drug doses administered, total amount of study drug exposure. Additional details will be provided in the SAP.

10.3.2.3.5 Exposure to Other Protocol-required Therapy

Descriptive statistics will be produced to describe the exposure to TCS following day 1 to end of study.

10.3.2.3.6 Exposure to Concomitant Medication

Number and proportion of subjects receiving therapies of interest will be summarized for each treatment group as coded by the World Health Organization Drug (WHODRUG) dictionary.

Appendix 1. List of Abbreviations and Definitions of Terms

Abbreviation or Term	Definition/Explanation
AD	atopic dermatitis
ALP	alkaline phosphatase
ALT	alanine aminotransferase
ANA	antinuclear antibody
AST	aspartate aminotransferase
AUC	area under the curve
AUC _{0-7d}	area under the curve from day 0 to day 7
AUC _{0-28d}	area under the curve from day 0 to day 28
CBC	complete blood count
CD	cluster of differentiation
CFR	Code of Federal Regulations
CIOMS	Council for International Organizations of Medical Sciences
C _{max}	maximum observed serum concentration
CPK	creatine phosphokinase
CRF	case report form
CRO	contract research organization
CTCAE	Common Terminology Criteria for Adverse Events
DILI	drug induced liver injury
DLQI	Dermatology Life Quality Index
EASI	Eczema Area and Severity Index
EASI 50	50% reduction from baseline in EASI score
EASI 75	75% reduction from baseline in EASI score
EASI 90	90% reduction from baseline in EASI score
ECG	electrocardiogram
eCRF	electronic case report form
EDC	electronic data capture
eDiary	electronic diary
Enrollment	A subject is considered enrolled when the investigator decides that the subject has met all eligibility criteria at the screening visit
End of Study (primary completion)	defined as the date when the last subject is assessed or receives an intervention for the final collection of data for the primary endpoint(s), whether the study concluded as planned in the protocol or was terminated early
End of Study (end of trial)	defined as the date when the last subject is assessed or receives an intervention for evaluation in the study (ie, last subject last visit), following any additional parts in the study (eg, long-term follow-up), as applicable

Abbreviation or Term	Definition/Explanation
End of Treatment	defined as the last assessment for the protocol-specified treatment phase of the study for an individual subject
EOI	event of interest
EOT	end of treatment
EQ-5D-3L	EuroQOL quality of life 5-dimensions 3-level version
eSAE	Electronic Serious Adverse Event
FSH	follicle-stimulating hormone
GCP	Good Clinical Practice
HIPAA	Health Insurance Portability and Accountability Act
HRT	hormonal replacement therapy
HRQoL	Health-Related Quality of Life
ICF	informed consent form
ICMJE	International Committee of Medical Journal Editors
IEC	Independent Ethics Committee
ICH	International Council for Harmonisation
ID	identification
IFN	interferon
Ig	immunoglobulin
IGA	Investigator's Global Assessment
IGA 0/1	response of 0 (clear) or 1 (almost clear) skin on IGA scale
IL	interleukin
IPIM	Investigational Product Instruction Manual
IRB	Institutional Review Boards
INR	international normalized ratio
IUD	intrauterine device
IUS	intrauterine hormonal-releasing system
Interactive Voice Response System (IVRS)	telecommunication technology that is linked to a central computer in real time as an interface to collect and process information
Interactive Web Response System (IWRS)	web based technology that is linked to a central computer in real time as an interface to collect and process information
LDH	lactate dehydrogenase
LKM1	liver kidney microsomal type 1
NASH	nonalcoholic steatohepatitis
NRS	numerical rating scale
PD	pharmacodynamics
PGI-S	Patient Global Impression of Severity
PI	principal investigator

Abbreviation or Term	Definition/Explanation
PK	pharmacokinetics
PRO	patient-reported outcome
POEM	Patient Oriented Eczema Measure
POR	Proof of Receipts
PPD	purified protein derivate
Q2W	every 2 weeks
Q4W	every 4 weeks
QFT-G	QuantiFERON-tuberculosis Gold
Randomization	A subject will undergo randomization upon meeting all eligibility criteria at the day 1 randomization visit
S. aureus	Staphylococcus aureus
SAP	statistical analysis plan
SAT	safety assessment team
SC	subcutaneous
SCORAD	Scoring of Atopic Dermatitis
Source Data	information from an original record or certified copy of the original record containing patient information for use in clinical research. The information may include, but is not limited to, clinical findings, observations, or other activities in a clinical trial necessary for the reconstruction and evaluation of the trial. Source data are contained in source documents (original records or certified copies). (ICH Guideline [E6]). Examples of source data include Subject identification, Randomization identification, and Stratification Value.
Study Day 1	defined as the first day that protocol-specified investigational product(s)/protocol-required therapies is/are administered to the subject
SUSAR	Suspected Unexpected Serious Adverse Reaction
TB	tuberculosis
TBL	total bilirubin
TCI	topical calcineurin inhibitors
TCS	topical corticosteroids
TSLP	thymic stromal lymphopoietin
ULN	upper limit of normal
WHODRUG	World Health Organization Drug Dictionary

Appendix 2. Clinical Laboratory Tests

The tests detailed in [Table 12-1](#) will be performed by the central laboratory and/or by the local laboratory.

Local laboratory results are only required in the event that the central laboratory results are not available in time for either study treatment administration and/or response evaluation. If a local sample is required, it is important that the sample for central analysis is obtained at the same time.

Protocol-specific requirements for inclusion or exclusion of subjects are detailed in [Sections 6.1](#) to [6.2](#) of the protocol.

Additional tests may be performed at any time during the study as determined necessary by the investigator or required by local regulations.

Table 12-1. Analyte Listing

Central Laboratory: Chemistry	Central Laboratory: Coagulation	Central Laboratory: Urinalysis	Central Laboratory: Hematology	Other Labs
Sodium	PT/INR	Specific gravity	RBC	Central Laboratory:
Potassium	APTT	pH	Nucleated RBC	Antibodies
Chloride		Blood	Hemoglobin	HLA typing
Bicarbonate		Protein	Hematocrit	Hep B surface antigen
Total protein		Glucose	MCV	Hep C antibody
Albumin		Bilirubin	MCH	HIV ^a
Calcium		WBC	MCHC	Skin biopsy ^b
Adjusted calcium		RBC	RDW	IgE
Magnesium		Epithelial cells	Reticulocytes	IgA
Phosphorus		Bacteria	Platelets	IgG
Glucose		Casts	WBC	IgM
BUN or Urea		Crystals	Differential	Serum Pregnancy
Creatinine			• Total Neutrophils	PPD or
Uric acid			• Eosinophils	Quantiferon Gold
Total bilirubin			• Basophils	Local Laboratory:
Direct bilirubin			• Lymphocytes	Urine Pregnancy
ALP			• Monocytes	
LDH			• Myeloblasts	
AST (SGOT)			• Promyelocytes	
ALT (SGPT)			• Myelocytes	
Cholesterol			• Metamyelocytes	
HDL			• Atypical lymphocytes	
LDL				
Triglycerides				

ALT = alanine aminotransferase; ALP = alkaline phosphatase; APTT = activated partial thromboplastin time;

AST = aspartate aminotransferase; BUN = blood urea nitrogen; HDL = high density lipoprotein;

Hep = hepatitis; HIV = human immunodeficiency virus; HLA = human leukocyte antigen; I

NR = international normalized ratio; LDH = lactate dehydrogenase; LDL = low density lipoprotein;

MCH = mean corpuscular hemoglobin; MCHC = mean corpuscular hemoglobin concentration;

MCV = mean corpuscular volume; PT = prothrombin time; RBC = red blood cell count;

RDW = Red cell distribution width; SGOT = serum glutamic-oxaloacetic transaminase;

SGPT = serum glutamic-pyruvic transaminase; WBC = white blood cell count

^a HIV assessment is recommended.

^b Skin biopsy may be sent to a central lab for holding, then sent to a specialty lab for analysis.

Laboratory/analyte results that could unblind the study will not be reported to investigative study centers or other blinded personnel until the study has been unblinded. Only eosinophils on complete blood count and differential are considered unblinding data for this study and will not be reported to the site post-randomization.

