9.2.2 Efficacy Assessments

9.2.2.1 Investigator's Global Assessment

The IGA allows investigators to assess overall disease severity at 1 given time point and consists of a 5-point severity scale from clear to severe disease (0 = clear; 1 = almost clear; 2 = mild disease; 3 = moderate disease; 4 = severe disease; 5 = very severe disease). The IGA uses clinical characteristics of erythema, infiltration, papulation, oozing, and crusting as guidelines for the overall severity assessment (Breuer et al, 2004). The IGA will be assessed at every visit according to the Schedule of Activities (Table 2-1 and Table 2-2). Whenever possible, the IGA should be assessed by the same investigator at each visit to reduce inter-rater variability.

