9.2.4 Clinical Laboratory Assessments

Refer to [Appendix 2](#) for the list of clinical laboratory tests to be performed and to the Schedule of Activities for the timing and frequency.

The investigator is responsible for reviewing laboratory test results and recording any clinically relevant changes occurring during the study in the Event CRF. The investigator must determine whether an abnormal value in an individual study subject represents a clinically significant change from the subject's baseline values. In general, abnormal laboratory findings without clinical significance (based on the investigator's judgment) are not to be recorded as adverse events. However, laboratory value changes that require treatment or adjustment in current therapy are considered adverse events.

Where applicable, clinical sequelae (not the laboratory abnormality) are to be recorded as the adverse event.

All protocol-required laboratory assessments, as defined in [Appendix 2](#), must be conducted in accordance with the laboratory manual and the Schedule of Activities.

Laboratory/analyte results that could unblind the study will not be reported to investigative study centers or other blinded personnel until the study has been unblinded. Only eosinophils on complete blood count and differential are considered unblinding data for this study. Additional details regarding potentially unblinding data and study personnel are provided in [Section 7.3.2](#).

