**Analysis Window for Hematology, Chemistry, Urinalysis (dipstick)**

Visit Week	Target Day	Window Definition
Baseline	1	
Week 12	85	Study Day 2 to 126
Week 24	169	Study Day 127 to 210
Week 36	253	Study Day 211 to 294
Week 48	337	Study Day 295 to 350
Week 52	365	Study Day 351 to 385
Week 58	407	Study Day 386 to 448
Week 70	491	Study Day 449 to 494

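### Withholding eosinophils alone leaves them recoverable by subtraction, if sites receive the rest of the blood count, before the week-16 investigator ratings

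*Protocol*

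**What the plan says.** Protocol Section 9.2.4 keeps potentially unblinding laboratory results from study centers until the study is unblinded, and then defines what that means for the blood count: "Only eosinophils on complete blood count and differential are considered unblinding data for this study". Appendix 2 repeats the rule and adds its timing: "Only eosinophils on complete blood count and differential are considered unblinding data for this study and will not be reported to the site post-randomization".

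Table 12-1 in Appendix 2 lists the haematology panel. It includes the total white count ("WBC = white blood cell count") and a differential with "Total Neutrophils", eosinophils, basophils, lymphocytes, monocytes and several immature or atypical forms. Neither document withholds any of these other than eosinophils.

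Section 9.2.4 also says: "The investigator is responsible for reviewing laboratory test results and recording any clinically relevant changes occurring during the study in the Event CRF".

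On the ratings, Section 9.2.2.1 says: "Whenever possible, the IGA should be assessed by the same investigator at each visit to reduce inter-rater variability". Section 9.2.2.2 asks the same for EASI. Neither document provides an efficacy assessor who is kept away from laboratory reports.

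Other masking exists. A footnote to Table 2-1 redacts immunoglobulins, including IgE, from laboratory reports, and Section 9.2.5 withholds drug concentrations.

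**The concern.** The protocol itself decides that eosinophils can reveal treatment. A differential is a partition of the white count, so hiding one part while showing the total and all the other parts does not hide it. The screening eosinophil count precedes randomization and is outside the mask, so a site would have a value to compare with.

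Both primary endpoints rest on investigator judgement. IGA 0/1 and EASI 75 are rated at the site, and rescue in Part A is at the investigator's discretion (Section 7.1.5). Under SAP Section 5.5, topical rescue from day 29 to week 16 makes a subject a non-responder. An investigator who can form a view of the arm could, without intending to, shift the rating or a late rescue decision.

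**Working it through.** There is no stated figure to reproduce. The check has four steps.

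**1. Can the value be derived?** The identity is

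eosinophils = WBC − (neutrophils + lymphocytes + monocytes + basophils + any immature or atypical cells),

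or 100% minus the other percentages. With assumed counts in 10⁹/L: 7.00 − (4.20 + 1.75 + 0.50 + 0.05) = 0.50, that is 500 cells/µL.

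**2. How precisely?** The documents do not give the reporting format. Worst-case rounding error, with WBC and four other cell types reported:

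| Assumed format | Calculation | Error (cells/µL) |
|---|---|---|
| Counts, 2 decimals | 5 × 0.005 × 1000 | ±25 |
| Counts, 1 decimal | 5 × 0.05 × 1000 | ±250 |
| Percentages to 0.1%, WBC 4 to 11 | 4 × 0.05% = 0.2% of WBC | ±8 to ±22 |
| Whole percentages, WBC 4 to 11 | 4 × 0.5% = 2% of WBC | ±80 to ±220 |

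For scale, SAP Section 9.4 splits baseline eosinophils at 300 cells/µL. The derived value is sharp in the finer formats and coarse in the others.

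**3. When, and which decisions?** SAP Appendix A gives the first post-baseline haematology window, labelled week 12, as "Study Day 2 to 126", with target day 12 × 7 + 1 = 85. Week 12 is therefore the only scheduled on-treatment count before week 16.

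- The week-16 target is 16 × 7 + 1 = day 113, so the gap is 28 days. With ±3-day visit windows it is at least 28 − 6 = 22 days.
- The rescue window that counts against response runs from day 29 to day 113, which is 84 days. Of these, 85 − 29 = 56 days, two thirds, come before the week-12 draw and cannot be affected.
- What is exposed before the primary endpoint is the week-16 IGA and EASI ratings and any rescue after the week-12 results return.

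**4. Can the effect be sized?** Not from the documents, which give no drug effect on eosinophils. For illustration only, assume a fall of 30% to 70% on active treatment and normally distributed log change. The chance that an active subject shows the larger fall than a placebo subject is Φ(d / (s√2)), where d = −ln(1 − fall) and s is the SD of the log change.

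- If s is 0.35 to 0.5: Φ(0.357 / (0.5√2)) = 0.69 to Φ(1.204 / (0.35√2)) = 0.99.
- If 0.35 to 0.5 is the SD of each measurement, then s is √2 times larger: Φ(0.357 / 1.0) = 0.64 to Φ(1.204 / 0.7) = 0.96.

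Both ranges ignore rounding, and neither is a bias in IGA or EASI. They run from weak to almost complete separation, depending wholly on the assumptions, so they should not be cited as the size of the problem.

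**The case against.** Five points can fairly be made for the plan.

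- **Release is inferred.** Table 12-1 lists tests performed, not the content of site reports, and the laboratory manual, which was not available, may suppress more. This stands as a caveat. But the protocol names eosinophils alone and requires investigators to review results, so its plain reading is that the other lines are sent.
- **General rules already bar potentially unblinding information** (Sections 7.3.2 and 9.2.4). They do not close the gap, because Section 9.2.4 goes on to limit unblinding blood-count data to eosinophils.
- **Eosinophils are not the only masked result.** Correct: immunoglobulins and drug concentrations are withheld too. The gap lies within the blood count.
- **Local laboratories are a minor route.** Appendix 2 does say its tests "will be performed by the central laboratory and/or by the local laboratory", and lets investigators order extra ones. But Table 12-1 places haematology with the central laboratory, and local results are required only when central ones would be late.
- **The mask still prevents casual disclosure.** Someone would have to do the subtraction deliberately, from a single variable sample. That is so; the mask is incomplete, not worthless.

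A reader might infer more: that sites were in fact unblinded, that the primary results are biased, or that all rescue decisions are open to influence. The documents support none of these. They show no release of the lines, no eosinophil effect and no influence on ratings, and rescue before the week-12 draw is out of reach.

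**Conclusion.** The point holds as a gap in the masking rule. As written, the protocol withholds one differential line that it considers unblinding and leaves in place everything needed to derive it, 28 days before the investigator-rated primary endpoints. This rests on two assumptions: that site reports carry the remaining lines, and that the reporting format is fine enough for the difference to be informative. It is a route to potential unblinding. Its effect on IGA 0/1 and EASI 75 cannot be quantified from the documents, and the sample size and alpha are untouched. Because the remedy is cheap and the endpoints are subjective, the change is worth making.

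**What to change.** In Section 9.2.4 and Appendix 2, state that after randomization enough differential lines are withheld from site reports to prevent eosinophils being derived by subtraction. That means at least monocytes and basophils as well as eosinophils, in both absolute and percentage form. Have the central laboratory alert sites to clinically important values in the withheld lines. Apply the same rule to any local or investigator-ordered differential where feasible. If the laboratory manual already does this, the protocol should say so.

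The cost is report configuration, and redaction is already in use for immunoglobulins. Sites lose routine sight of two minor lines and rely on alerts.

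The minimum version blocks exact recovery but leaves some information. With the counts assumed above, the visible remainder is 0.50 + 0.50 + 0.05 = 1.05. An assumed halving of eosinophils would move it to 0.80, a drop of 0.25/1.05 = 24%. Withholding lymphocytes as well makes the remainder 2.80 and the drop 0.25/2.80 = 9%, at the price of hiding a line that sites may want for safety review. Having IGA and EASI rated by someone who does not see laboratory reports would leave safety reporting intact, but it needs extra staff at about 100 centers and does not by itself cover rescue decisions.
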